Figure 13A-E: This figure shows the outcomes of patients treated with tocilizumab for cABMR and TG are shown and described above. 36 patients were treated with tocilizumab monthly for 6-25 months and 39 patients received standard of care (SOC) treatment (IVIG + rituximab +/- PLEX) and constitute the retrospective cohort. Tocilizumab patients have been followed for up to 6 years. There are now 54 patients in this cohort. This data supports the idea that interruption of the IL-6/IL-6R signaling pathway may be important in treating patients with severe cABMR and TG mediated by HLA antibodies. In addition, we see an important reduction of DSAs over time that would indicate a potential benefit in desensitization treatments. Figure 13A shows the graft survival of all patients from index biopsy. Tocilizumab patients have superior graft survival. In 13B, we see the survival of patients with TG where 82% of tocilizumab treated patients' graft were functioning at 6 years. Figure 13C shows the graft survival for patients who lost their grafts >3M after index biopsy and figure 13D shows a near significant benefit in increasing patient survival. In figure 13E, 9 patients who received tocilizumab at index biopsy and had repeat biopsies at 1 year are shown. We compared scores for inflammation and chronicity. Briefly, tocilizumab patients showed reductions in C4d+ staining and g + ptc scores, features which are commonly associated with a worse prognosis.

2.0 Clazakizumab (anti-IL-6) as a Potential Agent to Treat cABMR and TG

Clazakizumab (CSL Behring LLC., King of Prussia, PA) is a humanized monoclonal antibody aimed at the cytokine IL-6 ligand. Clazakizumab has been evaluated extensively in patients with rheumatoid arthritis, but has not yet been approved by the FDA for any condition. Since the introduction of IL-6/IL-6R blocking drugs, reports indicate that inhibition of the IL-6/IL-6R pathway may have significant benefits in SLE and other vasculitic disorders and reduces antibody producing cells in treated patients. There is currently no information for Clazakizumab in HS patients awaiting incompatible (HLAi) transplants or for treatment of antibody-mediated rejection.

Clazakizumab is a genetically engineered humanized immunoglobulin G1 (IgG1) antibody that binds to human IL-6 with an affinity of 4 pM. Using multiple assays for signaling and cellular functions in response to IL-6 alone (to measure classical signaling) and a combination of IL-6 and sIL-6R (to measure trans-signaling), it was demonstrated that clazakizumab is a potent and full antagonist of IL-6-induced signaling as measured by phosphorylation of signal transducer and activator of transcription 3 (STAT3), as well as cellular functions such as cell proliferation, differentiation, activation, B-cell production of immunoglobulins, and hepatocyte production of acute phase proteins (C-reactive protein [CRP] and fibrinogen). In addition, clazakizumab is shown to be a competitive antagonist of IL-6-induced cell proliferation. This in vitro pharmacological profile supports the potential of clazakizumab to impact multiple immune and non-immune cellular processes that are central to disease pathogenesis, and thus, to offer a new therapeutic modality in the treatment of autoimmune diseases and other IL-6 mediated diseases.

The clazakizumab development program includes a comprehensive nonclinical development program and clinical studies conducted in healthy subjects and in subjects with RA, psoriatic arthritis (PsA), Crohn's disease, graft-versus-host disease (GVHD), and oncology. To date, no studies with clazakizumab have been conducted in subjects with highly sensitized patients undergoing renal transplant, although supporting safety data are available from the previous clinical studies.

Nonclinical Studies

A comprehensive nonclinical development program has been completed. Clazakizumab was shown to be a potent inhibitor of IL-6-induced acute phase proteins. In pharmacokinetic (PK)/pharmacodynamic (PD) studies, a single dose of clazakizumab resulted in full inhibition of IL-6 activity as measured by the inhibition of IL-6-induced phosphorylated STAT3 (pSTAT3) activity in whole blood treated ex vivo with IL-6. The results of this functional PD assay correlated with drug exposures where full inhibition of pSTAT3 activity was observed when drug levels exceeded 50 ng/mL (approximately 0.3 nM). In a tissue cross-reactivity study, tissue binding of clazakizumab was observed in multiple tissues in both human and cynomolgus monkey, was generally cytoplasmic in nature, and was consistent with the known expression of IL-6 by cells and tissues. Results from both single- and repeat-dose nonclinical toxicology studies of up to 6 months in cynomolgus monkeys demonstrated an acceptable safety profile for clazakizumab. In a preliminary enhanced pre- and post-natal development (ePPND) study conducted in cynomolgus monkeys, an increase in the number of monkeys with retention of the placenta at parturition was observed at clazakizumab doses of 3 mg/kg (n=2) and 30 mg/kg (n=3), corresponding to doses 11 and 110 times the planned human dose of 50 mg. There were no other safety findings of clinical concern.

Clinical studies

Clinical studies have been conducted in healthy subjects and in the following patient populations: RA, PsA, CD, graft-versus-host disease (GVHD), and oncology. These clinical studies include a total of 1,223 subjects, of which 888 subjects were exposed to clazakizumab with doses ranging from 1 mg to 640 mg given by either intravenous (IV) or subcutaneous (SC) injection for up to 48 weeks.

Clinical Pharmacology

Following the administration of clazakizumab as a 1-hour IV infusion, the PK of clazakizumab were linear over the dose ranges of 30 mg to 640 mg in healthy subjects and 80 mg to 320 mg in subjects with RA as indicated by consistent clearance at these dose levels. The T-half of clazakizumab at all doses was very similar in healthy male subjects and in subjects with RA and was consistent with that expected for a humanized IgG1 antibody. Across the doses studied, the mean T-half of clazakizumab ranged from 19.5 to 31.0 days in healthy male subjects and from 26.4 to 30.9 days in subjects with RA. The T-half of clazakizumab after SC administration in healthy male subjects was similar to the IV administration. In a Phase 1 study comparing IV and SC dosing in healthy male subjects, the mean T-half of clazakizumab

was 30.7 days after a single IV dose and, 31.1 to 33.6 days after SC administration. The bioavailability of clazakizumab after SC administration was 60% of the IV formulation. As expected, Cmax was lower and Tmax was longer for the SC administration relative to IV administration.

Population PK analysis of the data from clinical studies in RA, PsA and healthy subjects have indicated that body weight affects the PK of clazakizumab such that both clearance and central volume of distribution increase with increasing body weight. Therefore, heavier subjects will have lower drug exposure compared with less heavy subjects.

Clinical Efficacy and Safety Studies

Efficacy and safety data for clazakizumab is available from clinical studies conducted in RA, PsA, and oncology. Studies conducted in GVRD and Crohn's disease were prematurely terminated due to safety concerns and therefore no efficacy conclusions are available for these studies.

In Phase 2 studies in RA and PsA, doses from 5 mg SC once every 4 weeks (Q4W) up to 320 mg IV once every 8 weeks were significantly effective with clinical response evident as early as 12 weeks post treatment. One study in RA also demonstrated that the efficacy of clazakizumab is comparable or may be better than the standard of care treatment (adalimumab + methrotrexate (MTX)) in RA.

Efficacy with clazakizumab was not shown in the 2 Phase 2 studies in oncology (head and neck cancer and non-small cell lung cancer).

Two studies were terminated prematurely due to safety concerns. A Phase 2 study in Crohn's was terminated early because of GI perforation in 3 subjects who had received clazakizumab and this indication is no longer being studied. Although these subjects had multiple confounding medical issues, and the disease itself has an inherent risk of mucosal perforation, gastrointestinal perforations were also observed during the clinical studies with tocilizumab in patients with RA. Gastrointestinal perforation is a recognized risk of anti-IL-6 mAbs. After only 3 subjects were enrolled, a study in subjects with GVHD was also prematurely terminated due to 2 subjects experiencing similar serious adverse events (SAEs) (i.e., acute renal failure) which led to death. Both subjects had severe GVHD disease at the time of death.

Overall, the safety findings from the clinical studies conducted with clazakizumab to date are consistent with the known effects of blocking the IL-6 pathway (see Actemra® prescribing information]). Identified risks associated with clazakizumab administration include the following: infections, liver function test (LFT) abnormalities, changes in hematology parameters (i.e., neutropenia and thrombocytopenia), dyslipidemia (i.e., hypercholesterolemia and hypertriglyceridemia), and gastrointestinal perforations.

For further details regarding clinical studies with clazakizumab, please consult the Investigator's Brochure.

3.0 Primary Objectives

This study will be an open label design to assess the safety and efficacy of clazakizumab 25 mg SC given every 4 weeks (30 days) for a total of 6 doses in eliminating DSAs and stabilizing clinical features of cABMR in patients who have biopsy proven severe cABMR +TG. If improvements are seen in pathologic features of antibody mediated rejection from this biopsy compared to index biopsy, we will offer patients the opportunity to continue clazakizumab administrations monthly for an additional 6 months. A one year biopsy will then be performed at the end of the study. Safety determinations will be aimed at assessments of any side effects associated with clazakizumab administration and risk for infectious complications associated with clazakizumab therapy. Limited efficacy determinations will include assessment

of composite surrogate end points including patient and graft survival, stabilization of the clinical features of cABMR (eGFR, SCr) after clazakizumab treatment, and safety throughout study duration.

Long term primary objectives include:

- 1. assess the safety and efficacy of clazakizumab 12.5 mg or 25 mg SC given every 4-8 weeks in eliminating DSAs and stabilizing clinical features of cABMR in patients who have biopsy proven severe cABMR +TG
- 2. assess composite surrogate end points including patient and graft survival, stabilization of the clinical features of cABMR (eGFR, SCr) after clazakizumab treatment, and safety throughout study duration

3.1 Major Secondary Objectives

In addition to our efforts to determine if clazakizumab treatment can significantly reduce or eliminate the severity of cABMR episodes and modify pathologic features (Banff 2015) at the end of 6 months of clazakizumab therapy, we will assess allograft function up to 6-12 M post-transplant, determine renal function using SCr, MDRD GFR (Schwartz equation will be used to estimate CrCl for patients under 18 years of age) calculations and DSA levels. A protocol biopsy will be performed at 6M post-clazakizumab therapy and 12M (for patients who receive 12 doses of clazakizumab). We will also record any late cABMR episodes after clazakizumab therapy. In addition, several immunologic determinations will be assessed at time points before and after initiation of clazakizumab therapy. These include the following:

- Assessment of T_{reg} cells (CD4+,CD25+,FoxP3+CD127^{dim})
- Assessment of T_{fh} cells (CD4+,ICOS+,CXCR5+, IL-21+)
- Assessment of circulating plasmablast (CD19+, CD38+,CD27+, IL-6+)
- > Assessment of CRP, IL-6 levels and Quantitative immunoglobulins by ELISA pre- and post-treatment for cABMR
- Viral PCR monitoring by center protocol for EBV, CMV and Polyoma BK

This study protocol is shown in Figure 14. These secondary end points will help us understand the biology of alloimmune responses to allografts and to determine the ability and mechanisms of clazakizumab's beneficial effects. We will also monitor viral PCRs as per standard-of-care. Long term secondary objectives include:

- 1. determine renal function using SCr, eGFR
- 2. DSA levels
- 3. A protocol biopsy will be performed at 12M, 24M post-clazakizumab LTE.
- 4. record any late cABMR episodes after clazakizumab therapy.
- 5. Assessment of CRP and IgG
- Viral PCR monitoring by center protocol for EBV, CMV and Polyoma BK

3.2 Inclusion Criteria

- ✓ Age 15-75 years at the time of screening.
- ✓ Biopsy proven cABMR with TG on biopsy as defined by Banff 2015 and DSA + at time of biopsy
- ✓ Subject/Parent/Guardian must be able to understand and provide informed consent.
- ✓ Pneumococcal vaccinated
- ✓ Negative tuberculin ppd result or negative Quantiferon TB gold

3.3 Exclusion Criteria

- ✓ Multi-organ transplant (e.g. kidney and pancreas)
- √ eGFR < 30 mL/min/1.73m²
- ✓ Advanced Transplant Glomerulopathy (CG3) or advanced IFTA (ct or ci scores ≥3)
- ✓ Previous allergic reactions to monoclonal antibodies.
- ✓ Lactating or pregnant females.

- ✓ Women of child-bearing age and male partners of women of child-bearing age who are not willing or able to practice FDA-approved forms of contraception during study and for 5 months after last dose.
- ✓ HIV-positive subjects.
- ✓ Subjects who test positive for HBV by HBVeAg/DNA or HCV infection [positive Anti-HCV (EIA) and confirmatory HCV RIBA].
- ✓ Subjects with latent or active TB. Subjects must have negative Quantiferon TB gold test result.
- ✓ Recent recipients of any licensed or investigational live attenuated vaccine(s) within two months of the screening visit (including but not limited to any of the following:
 - o Adenovirus [Adenovirus vaccine live oral type 7]
 - Varicella [Varivax]
 - Hepatitis A [VAQTA]
 - Rotavirus [Rotashield]
 - Yellow fever [Y-F-Vax]
 - Measles and mumps [Measles and mumps virus vaccine live]
 - Measles, mumps, and rubella vaccine [M-M-R-II]
 - Sabin oral polio vaccine
 - Rabies vaccines [IMOVAX Rabies I.D., RabAvert])
- ✓ A significantly abnormal general serum screening lab result defined as a WBC < 3.0 X 10³/ml, a Hgb < 8.0 g/dL, a platelet count < 100 X 10³/ml, an SGOT or SGPT > 3X upper limit normal
- ✓ Individuals deemed unable to comply with the protocol.
- ✓ Subjects with active CMV or EBV infection as defined by CMV-specific serology (IgG or IgM) and confirmed by quantitative PCR with or without a compatible illness (Quantitative PCR cut off defined as having > 50 copies of CMV or EBV DNA/PCR)
- ✓ Use of investigational agents within 4 weeks of participation.
- √ History or active Inflammatory Bowel Disease or Diverticular Disease or gastrointestinal perforation
- ✓ Recent infection (within past 6 weeks of screening) requiring any antibiotic use (oral, parenteral or topical).
- ✓ Present or previous (within 5 years) malignancy except for basal cell carcinoma, fully excised squamous cell carcinoma of the skin or non-recurrent (within 5 years) cervical carcinoma-in-situ.

4. Study Design & Methods

Background: This is a single center, Phase I/II, open label single-arm exploratory study. The trial will primarily examine the safety and tolerability of clazakizumab given after the diagnosis of cABMR in 10 subjects (15-75yrs) who exhibit DSAs to their donor. Patients entered will also have been diagnosed with cABMR + TG post-transplant based on Banff 2015 criteria. Patients are required to have a eGFR \geq 30 mL/min/1.73m² as calculated by the MDRD equation (Schwartz equation will be used to estimate CrCl for patients under 18 years of age) at entry. All patients will be recruited from the renal transplant program at Cedars-Sinai Medical Center. Once cABMR is diagnosed, donor-specific anti-HLA antibodies will be assessed (DSA) which are associated with cABMR and/or graft loss. DSA will be detected using solid phase assay systems currently utilized at the Cedars-Sinai Medical Center HLA Laboratory ([name] Director, [contact]. These anti-HLA antibodies may result naturally or from previous pregnancy, transfusions, or prior transplants. Patients treated with clazakizumab for cABMR will have labs for DSAs, and other monitoring labs as well as immunologic studies as outlined (See Study Protocol in Appendix A). In addition to the standard post-transplant immunosuppressive protocol, patients with cABMR will receive clazakizumab 25mg SC given every 4 weeks (30 days) for a total of 6 doses. If no safety/tolerability/efficacy issues are observed after the initial dose, patients will continue the protocol as outlined (see Appendix A). A protocol biopsy will be performed after the 6th and after the 12th doses of clazakizumab (as mentioned before) to assess the allograft for evidence of cABMR/ABMR, including C4d staining and TG using Banff 2015 criteria¹⁴. Banff scoring will be compared between the index and protocol biopsy after cessation of therapy. Patients who have evidence of persistent allograft dysfunction may have non-protocol biopsies for cause. After completion of the clazakizumab therapy, patients will be followed up to assess allograft function and ABMR episodes as well as DSAs. The protocol is summarized in figure 14 below. Monitoring of Treg, Thir, Tfh and plasmablast as well as IL-6

and CRP level will be performed in the Transplant Immunology Lab at Cedars-Sinai Medical Center at select time points ([name] Director, [contact]).

[figure not shown]

Figure 14: This figure shows the protocol designed to investigate the safety and efficacy of clazakizumab in treating cABMR + TG. The study is open label, single center one-arm study that will enter patients diagnosed with cABMR + TG by renal biopsy and who have eGFR of > 30cc/min at time of diagnosis. Entered patients will receive clazakizumab 25mg every 4 weeks (30 days) for a total of 6 doses. If patients show improvement (ie: eGFR/DSA/biopsy/PI confirmation) they will continue monthly clazakizumab for an additional 6 months and will have a second biopsy at 12 month protocol. Immunologic and viral monitoring labs will be performed as indicated. For those continuing in the long term extension, the day 365 visit will be followed by visits every 4-8 weeks.

The subjects will be followed to determine if the use of clazakizumab for treatment of cABMR in this high-risk transplant population is safe and without infectious risks. In addition, we will determine the effects of clazakizumab treatment on renal biopsy assessments performed at 6 months. Assessments of renal function, donor specific antibody, and Banff 2015 biopsy scores will be evaluated at that time. If improvement or stabilization observed, clazakizumab will be resumed monthly x 6 doses (starting day 180 to day 330) and last study visit will be day 365 with biopsy for those who are not continuing to the long term extension. For those continuing in the long term extension, the day 365 visit will be followed by visits every 4- 8 weeks, per the schedule in Appendix E. We will assess the transplanted patients to determine the number who sustain a viable and functioning kidney allograft as well. In the event a patient does not show improvement after receiving 6 doses of clazakizumab, no further treatment will be given and the patient will return at Day 365 for a final study visit. All subjects will be evaluated on an intent-to-treat basis. The subject accrual rate will be limited to 2 patients for the initial dosing appointment. Once the first 2 patients have received their first injection, 2-4 patients may be screened per month until all 10 patients are enrolled. Repeat laboratories will be performed at the completion of clazakizumab therapy to determine effect on levels and correlation with any potential events. A detailed analysis of the study is discussed below.

A long term dosing option at conclusion of 12 months (after Study Day 365 visit) For those patients who complete the 12 month protocol, patients may continue to receive clazakizumab 12.5 mg or 25 mg subQ, dosed every 4-8 weeks long term, per PI discretion. Please see Appendix E for long term visit schedule. Biopsies during the long term extension will Page 21

be conducted at 12 months per PI discretion or for cause (suspected rejection). The long term extension of this study is planned as an ongoing protocol, with patients to continue in the LTE if approved on an annual basis by PI and CSL Behring. Participants in the LTE component of the study will be removed if it is determined that there is no longer a clinical benefit of therapy or if there is an observed issue with safety. The LTE will be allowed until clazakizumab is FDA approved in the US or if the study is terminated. The objectives for the LTE are included in Sections 3 and 3.1. Physical exams during the LTE will occur in person or via Video Visit, as per SOC protocol.

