If a patient has symptoms of anaphylaxis or serious hypersensitivity, or requires an interruption of the study drug because of symptoms of anaphylaxis or hypersensitivity, administration of clazakizumab must be discontinued permanently. The patient should be treated according to the standard of care for management of the hypersensitivity reaction. A blood sample for the presence of anti-clazakizumab antibodies should be obtained.

Clazakizumab should not be administered to subjects who have had any previous allergic reactions to monoclonal antibodies. To date, no infusion reactions have been associated with clazakizumab administered by IV infusion. Injection site reactions have been reported with SC administration. Reactions have been mild or moderate and have resolved without treatment. Both allergic reactions and injection site reactions should be treated with standard of care. Subjects who have developed significant allergic reaction to study drugs should not be re-challenged.

Viral Reactivation

Though rarely reported within the clazakizumab program due to exclusion criteria at study entry, reactivation of viral and other serious infections (e.g. EBV or TB) has been observed with biologic therapies.

Drug Interaction

The formation of CYP450 enzymes may be suppressed by increased levels of cytokines (eg, IL-6) during chronic inflammation. Therefore, it is expected that for molecules that antagonize cytokine activity, such as clazakizumab, the formation of CYP450 enzymes could be normalized. When starting or stopping therapy with clazakizumab, patients taking medications which are individually dose-adjusted and metabolized via CYP450, 3A4, 1A2, or 2C9 (e.g. atorvastatin, calcium channel blockers, theophylline, warfarin, phenytoin, cyclosporine, or benzodiazepines) should be monitored as doses may need to be adjusted to maintain their therapeutic effect. Given its long elimination half-life (t1/2), the effect of clazakizumab on CYP450 enzyme activity may persist for several weeks after stopping therapy.

Pregnancies and Women of Child Bearing Potential

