A total of 9 pregnancies were reported from the clazakizumab completed clinical studies. Eight were exposed to clazakizumab, and 1 to placebo. Of the 8 pregnancies that were exposed to clazakizumab, 5 were maternal exposure and 3 were paternal exposure. Eight pregnancies occurred in subjects enrolled in rheumatoid or psoriatic arthritis studies, who received concomitant low-dose MTX which is a known human teratogen with an increased risk of spontaneous abortions, intrauterine growth restriction, and congenital malformations in case of exposure during pregnancy. (https://www.medicines.org.uk/emc/product/511/smpc)

The outcomes after maternal exposure were as follows:

1 normal newborn, 2 spontaneous abortions, 1 missed abortion, and 1 intrauterine growth retardation.

The outcomes after the paternal exposures were as follows:

1 spontaneous abortion, 1 unknown outcome, and 1 baby born with Mosaic Down's syndrome.

The investigator considered that 1 spontaneous abortion (Study IM133001) and the missed abortion (Study IM133004) after maternal exposure were related to clazakizumab and MTX treatment. All other pregnancy outcomes were considered as unrelated to clazakizumab.

In the US general population, the estimated background risk of major birth defects is 2% to 4% and the rate of miscarriage in clinically recognized pregnancies is 15% to 20% (https://www.fda.gov/media/90160/download).

Due to the confounding effect of MTX treatment and the general background risk of major birth defects and miscarriage in clinically recognized pregnancies, the role of clazakizumab is unknown.

Insufficient data is available from pregnancy exposure in clinical studies to date to inform on the potential harm of clazakizumab use during pregnancy. All subjects of child bearing potential being treated with clazakizumab (and their partners) must be informed of this risk, and use highly effective birth control. Administration of clazakizumab may decrease the efficacy of hormonal oral contraceptives.

Under no circumstances shall clazakizumab injection be administered to women known to be pregnant or lactating.

6 Therapy Stopping Points

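### The Section 3.3 contraception criterion is looser than the standard Section 5.3 sets for treated subjects, and it does not reflect the oral contraceptive warning

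*Protocol*

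**What the plan says.** Two places in the protocol set a contraception rule.

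- **Section 3.3 (Exclusion Criteria)** excludes women of child-bearing age, and men partnered with them, "who are not willing or able to practice FDA-approved forms of contraception during study and for 5 months after last dose". It does not grade methods and does not mention oral contraceptives. A separate criterion excludes "Individuals deemed unable to comply with the protocol".
- **Section 5.3 (Adverse Drug Reactions, pregnancy paragraphs)** says that all "subjects of child bearing potential being treated with clazakizumab (and their partners) must be informed of this risk, and use highly effective birth control". The next sentence is "Administration of clazakizumab may decrease the efficacy of hormonal oral contraceptives". No period is given, and nothing says what a site should do about the warning.

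The Drug Interaction paragraphs of Section 5.3 ask for monitoring of "patients taking medications which are individually dose-adjusted and metabolized via CYP450, 3A4, 1A2, or 2C9" when clazakizumab is started or stopped. Contraceptives are not among the examples. The same paragraph adds that "the effect of clazakizumab on CYP450 enzyme activity may persist for several weeks after stopping therapy".

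Appendices A and E schedule pregnancy tests and concomitant medication review, but the parts shown contain no contraception rule.

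**The concern.** Screening is where the method of contraception is checked before first exposure, and the rule applied there is weaker than the one the protocol sets for the same woman once she is treated. Taking an oral contraceptive to be an approved form, a woman who relies on it alone passes the contraception criterion in Section 3.3, although Section 5.3 says the study drug may weaken that method.

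The stake is pregnancy exposure. Section 5.3 states: "Insufficient data is available from pregnancy exposure in clinical studies to date to inform on the potential harm of clazakizumab use during pregnancy". It also bars dosing of women known to be pregnant. Pregnancy tests detect a pregnancy and stop further dosing, but prevention rests on contraception, so the rule should say the same thing wherever it appears.

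**Working it through.** No sample size, power or event count is involved, so the check is mainly a comparison of text.

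**1. The two rules side by side**

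| | Section 3.3 | Section 5.3 |
|---|---|---|
| Standard | Any FDA-approved form | Highly effective |
| Who | Women of child-bearing age; men partnered with them | Treated subjects of child-bearing potential; their partners |
| Period | During study plus 5 months after last dose | None stated; refers to subjects being treated |
| Oral contraceptives | Not mentioned | Efficacy may fall; no action |

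A method that is both FDA-approved and highly effective meets both rules. Section 5.3 does not define highly effective, so whether an oral contraceptive alone meets it, given the warning in the next sentence, is left to the reader.

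**2. Who is affected by the oral contraceptive point**

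Entry is "Age 15-75 years at the time of screening" (Section 3.2). Appendix E puts child-bearing age at 12 to 55. The overlap runs from max(15, 12) = 15 to min(75, 55) = 55 years. Only female subjects count, because partners of male subjects do not take the drug. Ten subjects are planned (Section 4). The number using only an oral contraceptive is not stated.

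**3. Pregnancy testing after the last dose (nominal days, Appendix A, no extension)**

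Tests are scheduled at screening and at every dosing visit. Taking 5 months as 150 days:

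- Twelve doses: last dose Day 330, last scheduled test Day 365. 365 − 330 = 35 days, leaving 150 − 35 = 115 days without a scheduled test.
- Six doses: last dose Day 150, test at Day 180 (30 days later), next at Day 365 (365 − 150 = 215 days later, beyond the 150).

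In much of this period contraception is the only stated safeguard.

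**4. Is the drug still present in that period?**

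Section 2.0 gives mean half-lives from 19.5 days (lowest, IV) to 33.6 days (highest, SC), with 31.1 to 33.6 days for SC dosing. Assuming simple exponential decline, fraction remaining = 0.5^(t / half-life):

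| t (days) | 19.5 d | 31.1 d | 33.6 d |
|---|---|---|---|
| 28 | 37.0% | 53.6% | 56.1% |
| 56 | 13.7% | 28.7% | 31.5% |
| 150 | 0.5% | 3.5% | 4.5% |

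This trial doses SC, so the two right-hand columns are the more relevant. The half-lives come from healthy and rheumatoid arthritis subjects, not transplant recipients. The figures show that exposure continues for weeks after the last dose, in line with the protocol's own remark on CYP450. They do not measure contraceptive failure.

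**The case against.** The strongest reply is that nothing here is contradictory. Section 5.3 is mandatory, its warning follows directly on the requirement, and a candidate who will not meet it can be excluded as unable to comply. The 5 months in Section 3.3 can be read as the period and Section 5.3 as the standard. Pregnancy tests and concomitant medication review at every dosing visit add further control. Consent pages and part of the notes to Appendix A are not in the text available and may list acceptable methods.

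Much of this stands. A reader might infer that the two sections conflict, or that the protocol authorises dosing a woman who relies on an oral contraceptive alone. The documents support neither: the rules are cumulative, and passing one exclusion criterion is not the same as meeting the whole protocol.

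What survives is narrower. The criterion that names the method at screening omits the protocol's own stronger standard. The warning has no action attached. Section 5.3 speaks of subjects being treated, so after the last dose only the looser wording has an explicit period. Reading the two sections together closes that last gap only if every site does so.

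**Conclusion.** The point holds as a minor safety harmonisation. Section 3.3 should carry the standard and the warning that Section 5.3 already contains. The gap lies at screening and in the roughly 150 days after the last dose; during treatment it is largely covered.

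Three further inferences should be avoided. The 5-month length is not shown to be too short: at most about 4.5% of the drug remains at 150 days under the stated assumption, and the adverse event reporting period is also 150 days. The interaction is given only as a possibility, so the protocol does not establish that oral contraceptives fail. And the concern does not extend to untreated partners of male subjects who use an oral contraceptive.

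The conclusion rests on the shown text of Sections 3.3 and 5.3 and on counting oral contraceptives as an approved form. The number of women affected is unknown and may be zero of ten. The long-term extension lengthens the time the wording applies, but no endpoint or analysis depends on it.

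**What to change.** In Section 3.3, replace the reference to FDA-approved forms with *highly effective birth control* and leave the existing period unchanged. Add a sentence limited to female subjects receiving clazakizumab: *Because clazakizumab may reduce their efficacy, oral hormonal contraceptives alone are not sufficient; a non-oral or additional method is required.* The limit matters, because applied to the whole criterion the sentence would wrongly bar male subjects whose untreated partners use an oral contraceptive.

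In Section 5.3, cross-refer to Section 3.3 for the same standard and the same 5 months.

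The cost is a reworded criterion, one added sentence and a cross-reference. The downside is that an occasional female candidate must change or add a method before enrolment.
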